
We have been approved for funding by Department of Defense (DoD) to support for a 4-year multicenter RCT of TH+NMB for 48h vs. standard of care with contract to be completed June 1, 2020 and with enrollment to begin in Fall of 2020. This study was designed prior to the onset of COVID-19, which is now the most common cause of ARDS and will likely continue to be in the Fall, 2020 and perhaps beyond. Therefore, it is important to decide whether patients with COVID-19 ARDS should be enrolled in our CHILL trial. Therefore, we will conduct a 20-patient pilot safety and feasibility trial of our CHILL TH+NMB treatment vs. control in COVID-19 patients with ARDS who meet the inclusion/exclusion criteria of our DoD-funded trial. The major objective of the proposed pilot trial is to determine whether it is safe and feasible to include patients with COVID-19 ARDS in our Phase IIb CHILL RCT of TH+NMB vs. control in patients with moderate to severe ARDS.

The pilot will be conducted at the University of Maryland Medical Center. To facilitate randomization within the inclusion window, we will consent and enroll based on partial fulfillment of randomization criteria and randomize once all criteria are met. Patients will be

eligible for enrollment when they have been diagnosed with COVID-19 by PCR, and have met all Berlin criteria for moderate to severe ARDS within the 48h inclusion window except the P/F ratio  $\leq 200$  but will not be randomized until P/F ratio (measured or imputed based on SpO2) is  $\leq 200$  (while on  $\geq 8$  cm H2O PEEP and  $\geq 0.6$  FiO2). We plan to randomize a total 20 patients over 4 months to hypothermia (core temperature 34°-35°C for 48h) plus NMB or usual temperature management. The primary outcome measures will be effectiveness of cooling in achieving and maintaining the target temperature and safety measures. Secondary outcomes will include 28-day ventilator-free days (VFDs), 28-day ICU-free days, oxygen saturation index (OSI), driving pressure, Sequential Organ Failure Assessment (SOFA) score, 60-day and 90-day survival, 90-day functional assessment, cognitive assessment at ICU and hospital discharge, and biomarkers of inflammation and lung injury. Since the nature of the intervention precludes blinding, all treatment and clinical decision making related to study outcomes will be protocolized and compliance with study protocols will be monitored.

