### 1.2/ Study Aims and Objectives

We will conduct the CHILL-pilot single-center RCT of TH in patients with COVID-19 and ARDS with P/F < 250 to address the following specific aims:

1. **Aim 1: Analyze the safety and feasibility and the potential lung protective effect of treating patients with COVID-19 infection and ARDS with P/F < 200 with mild TH (core temperature 34°-35°C) + NMB for 48h compared with controls receiving standard temperature management.** We expect the TH-treated group to achieve targeted temperature within 4h of randomization and to maintain TH for 48h without significant increase in serious adverse effects compared with the control arm.
2. **Analyze the potential lung protective effect of mild TH (core temperature 34°-35°C for 48h) and NMB in patients with ARDS and P/F < 200 compared with controls receiving standard temperature management.** We expect the TH-treated group to trend toward having more 28-day VFDs (primary) and 28-day ICU-FDs, and improved day-3 driving pressure and OSI than the controls.
3. **Evaluate the effects of TH on systemic inflammation and extrapulmonary organ dysfunction.** We expect the treated group to have reduced levels of proinflammatory mediators and lower Sequential Organ Failure (SOFA) scores than controls.

The proposed pilot study will determine whether we can safely include patients with COVID-19 and ARDS in our larger Phase IIb trial of TH and NMB in patients with ARDS. It will help us determine whether the 48h duration of cooling is sufficient.

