##### 2.1.3.1.2 Biomarker Core Procedures

1. Samples will be stored in a remotely monitored -80°C freezer with liquid CO2 back-up located in the University of Maryland Baltimore Health Science Facility-II in ancillary space adjacent to [name] basic research laboratory (Rm S116).
2. Labeled EDTA-anticoagulated blood samples from all participating ICUs will be transported on ice directly to [name] laboratory within 30 minutes of collection and processed as described in the Sample and Processing section. The [name] laboratory is adjacent to UMMC
3. Samples will be batched for assays to be performed every 4-6 months. [name], will hand-carry one aliquot in labeled cryotubes per blood draw in marked freezer boxes on ice to the Cytokine Core Laboratory located on the seventh floor of the adjacent Bressler Research Building.
4. Samples will be received by [name], Supervisor of the Cytokine Core Laboratory, who will place the samples in the Cytokine Core Laboratory remotely-monitored, liquid-CO2-backed-up -80°C freezer until she performs the planned immunologic assays.
5. All assays will be performed in the Cytokine Core Laboratory using in-house ELISAs (IL-1 $\beta$ , IL-6, IL-8, IL-18, and sTNFR1) or purchased ELISA kits (sRAGE, SP-D, sICAM-1, MMP8).
6. [name] is the Director of the University of Maryland Cytokine Core Laboratory and has weekly meetings with [name] to review throughput and quality of all projects in the Cytokine Core Laboratory. The progress of the CHILL-pilot analysis will be discussed as part of these weekly meetings.
7. [name] will analyze all CHILL-pilot biomarker data for reproducibility and monitor performance of all biomarker assays by inspecting the standard curve, monitoring within-assay coefficient of variance between replicate measurements, and between-assay coefficient of variance based on pre-aliquoted internal controls to be included on each assay plate.

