### 3.3/ Randomization

Subjects will be stratified by proning status at enrollment and randomized within each stratum to receive TH or usual temperature management using a 1:1 assignment ratio. Treatment group assignment will be made using an Excel-based assignment tool stored on the UMB Microsoft OneDrive, which records date, time, and investigator who makes the treatment assignment. Baseline APACHE II, Sequential Organ Failure (SOFA) score 3, driving pressure, P/F ratio, and oxygen saturation index will be documented at time of randomization to assess comparability of disease acuity between groups.

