**eTable 2: Imputed PF ratio (cells) for combinations of SpO2 (rows) and FiO2 (columns)**

	0.30	0.35	0.40	0.45	0.50	0.55	0.60	0.65	0.70	0.75	0.80	0.85	0.90	0.95	1.00
80%	148	127	111	98	89	81	74	68	63	59	55	52	49	47	44
81%	151	129	113	101	91	82	76	70	65	60	57	53	50	48	45
82%	155	132	116	103	93	84	77	71	66	62	58	55	52	49	46
83%	158	136	119	106	95	86	79	73	68	63	59	56	53	50	47
84%	162	139	122	108	97	89	81	75	70	65	61	57	54	51	49
85%	167	143	125	111	100	91	83	77	71	67	63	59	56	53	50
86%	171	147	129	114	103	94	86	79	73	69	64	61	57	54	51
87%	177	151	132	118	106	96	88	81	76	71	66	62	59	56	53
88%	182	156	137	121	109	99	91	84	78	73	68	64	61	58	55
89%	189	162	141	126	113	103	94	87	81	75	71	67	63	60	57
90%	196	168	147	130	117	107	98	90	84	78	73	69	65	62	59
91%	203	174	153	136	122	111	102	94	87	81	76	72	68	64	61
92%	213	182	159	142	128	116	106	98	91	85	80	75	71	67	64
93%	223	191	168	149	134	122	112	103	96	89	84	79	74	71	67
94%	236	202	177	157	142	129	118	109	101	94	89	83	79	75	71
95%	252	216	189	168	151	138	126	116	108	101	95	89	84	80	76
96%	273	234	205	182	164	149	136	126	117	109	102	96	91	86	82

Conditions required to use inferred P/F ratio include: (a) SpO2 values 80-96%, (b) SpO2 measured ≥10 min after FiO2 change, (c) PEEP ≥ 8 cm H2O, (d) adequate pulse oximeter wave form, and (e) qualifying inferred P/F ratio is confirmed 1-6 hrs after the initial determination.

P/F ratio criterion met within 7 ventilator days

- Yes Collect **baseline blood sample**, randomize and record randomization time and treatment assignment below
- No STOP

Is this patient currently receiving prone positioning alternating with supine positioning?

- Yes
- No

Randomization date/time:    /   /          
MONTH D D Y Y Y Y TIME (0-2400)

Treatment assignment (check one)

- Therapeutic Hypothermia
- Usual Treatment

Initiate sedation, NMB, and cooling protocol for subjects randomized to Therapeutic Hypothermia

Complete Baseline information CRF.

See schedule for first week blood and data collection below.

--	--

[figure not shown]
SITE ID

--	--	--	--

PATIENT ID

--	--	--

LETTER CODE

- Collect baseline blood and complete Baseline CRF based on 24h preceding randomization
- Collect day 1 blood and complete Day 1 CRF at 0800 on randomization day + 1; (the duration of day 1 may be 8h 1 min to 31h 59 min as indicated by the examples a - c)

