Pilot Randomized Clinical Trial of Therapeutic Hypothermia Plus Neuromuscular Blockade vs. Standard of Care in Patients With Moderate to Severe ARDS - the Cooling to Help Injured Lungs (CHILL) Pilot Study

NCT03376854

Statistical Analysis Plan

Date: May 19, 2020

Statistical Analysis Plan: This is a pilot study of feasibility to demonstrate feasibility and safety to treat patients with COVID-19 and ARDS with our CHILL treatment protocol (hypothermia to core temperature 34-35°C + NMB for 48h) and to determine whether there are any trends toward benefit in the treated group. The primary outcome will be analyzed using descriptive statistics, the mean \pm SD and the median \pm IQR of time to reach the target temperature and the percent of total treatment time within the targeted temperature range. Differences in SAEs will be analyzed by Chi square. The group difference on 28-day VFDs will be tested with a permutation test for the difference in group means with alpha = .05 (two-tailed). This test was chosen due to the large number of zero values expected (based on our open-label pilot and retrospective studies). If the difference on a baseline prognostic variable is statistically significant, we will perform a secondary analysis to adjust for this variable using a regression approach. For secondary clinical outcomes t-tests, Wilcoxon, or chi-square tests will be used as appropriate. Mixed model repeated measures ANOVA will be used to test for group differences for physiological and biomarker secondary outcomes over days 0, 1, 2, 3, 4, and 7. We will not include an interim analysis in this small RCT with only 20 subjects.

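### The SAP names no measurement scale for the nine plasma markers; if they are right-skewed, repeated-measures ANOVA on raw concentrations wastes precision that a stated log scale and baseline adjustment would recover.

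*SAP*

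**What the plan says.** The SAP is a single paragraph, and biomarkers get one sentence of it: "Mixed model repeated measures ANOVA will be used to test for group differences for physiological and biomarker secondary outcomes". That sentence gives the time factor as six nominal days, "over days 0, 1, 2, 3, 4, and 7". Day 0, the pre-treatment sample, is therefore one level of the outcome. The sentence names no transformation, covariance structure, baseline covariate or target contrast. The same sentence covers the physiological variables.

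Protocol 2.1.3.1.2 (Biomarker Core Procedures) lists the markers. It states "All assays will be performed in the Cytokine Core Laboratory using in-house ELISAs" for five of them (IL-1β, IL-6, IL-8, IL-18, sTNFR1) and purchased kits for four (sRAGE, SP-D, sICAM-1, MMP8). Protocol 1.2 (Study Aims and Objectives) gives the Aim 3 expectation: "reduced levels of proinflammatory mediators and lower Sequential Organ Failure (SOFA) scores than controls".

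On size, Protocol 1.1 says "We plan to randomize a total 20 patients over 4 months", and Protocol 3.3 randomizes within proning strata "to receive TH or usual temperature management using a 1:1 assignment ratio", which gives about 10 per arm.

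On timing, the schedule notes at the end of the Screening/Enrollment/Randomization form (Protocol Appendix) put the day 1 sample at 0800 on the day after randomization, so "the duration of day 1 may be 8h 1 min to 31h 59 min". The later samples are also fixed to 0800.

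**The concern.** In the same paragraph the SAP chooses a permutation test for ventilator-free days because many zeros are expected. It makes no such allowance for plasma concentrations, where a few very high values can dominate an arm mean when there are only 10 patients in the arm. If the marker distributions are right-skewed and treatment multiplies the level, a raw-scale ANOVA is an inefficient way to look for the effect that Aim 3 describes.

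Keeping day 0 as an outcome level has a second cost. No treatment effect can be present at day 0, so the group main effect is diluted and the group-by-day test has to carry the comparison.

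The omission also leaves the scale open until the data of 20 unblinded patients have been seen.

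**Working it through.** **The plan's own figure.** There is none. The documents state no power, effect size or SD for Aim 3. For context, 10 per arm gives 80% power in a plain two-group comparison at (1.96 + 0.84) × √(2/10) ≈ 1.25 SD.

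**Inputs from the documents.** 20 patients, 1:1; six sampling days (0, 1, 2, 3, 4, 7); nine markers.

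**Inputs assumed.** Log-normal concentrations; total log10 SD from 0.15 to 0.7; within-patient correlation 0.6; a true TH/control ratio of 0.5 (−0.301 on log10), constant after baseline; no missing samples; two-sided 0.05 (the SAP states alpha for ventilator-free days only).

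**Model.** log10 value = patient effect (variance 0.6 × SD²) + residual (variance 0.4 × SD²) − 0.301 for TH patients after day 0. The split-plot ANOVA (group F on 1 and 18 df; group-by-day F on 5 and 90 df) is run on the same simulated trials in raw and in log form.

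| log10 SD | Group-by-day, raw | Group-by-day, log | Post-baseline mean adjusted for day 0, log |
|---|---|---|---|
| 0.15 | 97% | 100% | about 100% |
| 0.3 | 39% | 68% | 95% |
| 0.5 | 10% | 26% | 59% |
| 0.7 | 4% | 14% | 34% |

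With no true effect, the raw-scale tests reject about 2 to 5% of the time, and the log-scale tests about 5%.

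If only the group difference in post-baseline means is tested, without baseline adjustment, the loss is smaller. Raw versus log power is 65% versus 72%, 22% versus 33% and 9% versus 20% at log10 SD 0.3, 0.5 and 0.7.

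**Why baseline adjustment helps.** The mean of five post-baseline values has variance SD² × (0.6 + 0.4/5) = 0.68 SD². After adjustment for day 0 this is SD² × (0.68 − 0.6²) = 0.32 SD². At log10 SD 0.5 the standardised difference rises from 0.301/(0.5 × √0.68) = 0.73 to 0.301/(0.5 × √0.32) = 1.06.

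**Sensitivity to correlation.** At natural-log SD 1.0 (log10 SD 1.0/2.303 = 0.43), raw versus log group-by-day power is 11% versus 20% at correlation 0.3, 15% versus 34% at 0.6 and 27% versus 64% at 0.8.

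**Sensitivity to time course.** The gain in the last column of the table relies on a constant effect. Suppose the effect instead builds over 24 h, holds to 52 h and decays to 25% by 120 h, with natural-log SD 0.8 and ratio 0.5. Log group-by-day power is then 53%, and baseline-adjusted power is 61% over all post-baseline days or 77% over days 1 to 3. With a constant effect the corresponding figures are 52% and, over all days, 88%.

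**Timing.** With samples at 0800, hours since randomization = 24 × day + 8 − clock hour of randomization. Day 1 runs from 24 + 8 − 24 = 8 h to 24 + 8 − 0 = 32 h. Day 2 runs from 32 to 56 h, which straddles the end of 48 h of cooling. With the time course above, natural-log SD 0.8 to 1.0 and ratio 0.4 to 0.5, this spread costs 1 to 3 points for the group main effect and 4 to 8 for group-by-day. It costs 15 to 23 points for a day 1 contrast, which the SAP does not plan.

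**The case against.** The strongest reply is that the SAP is silent on scale. A reader might infer that it has chosen raw concentrations, but it has not, and a mixed model fitted to log values would comply with it. That stands: the defect is an unstated scale, and the power loss follows only if the sentence is applied literally.

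Second, the loss is assumed. The documents give no marker distribution, and simulated log-normal data with a multiplicative effect must favour the log scale. This also stands. For nearly symmetric markers the loss is negligible (97% versus 100% at log10 SD 0.15), though logging then costs little.

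Third, at high variability the log scale does not rescue Aim 3: log-scale group-by-day power is still only 26% or 14% at log10 SD 0.5 or 0.7. That is correct, and it is why baseline adjustment belongs in the same edit.

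Fourth, this is a feasibility pilot looking for trends and it claims no power for these outcomes. That limits the importance of the point. It does not remove the case for fixing the scale beforehand, since a ratio with an interval describes a trend better than an ANOVA p-value dominated by a few high values.

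The width of the day 1 window might suggest that nominal day is an equally serious fault, to be cured by adding hours from randomization as a covariate. The sampling rule does not support that. Post-baseline hours are nominal day plus a per-patient constant, so the covariate cannot align exposure to hypothermia. In a check under the same kind of assumptions, it moved log-scale main-effect power from 0.41 to 0.39 at natural-log SD 0.7 and from 0.23 to 0.22 at 1.0.

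**Conclusion.** The point holds as an inexpensive improvement to an under-specified analysis. For a true halving, with log-normal data and correlation 0.6, using raw concentrations lowers group-by-day power by 29 points at log10 SD 0.3 (68 − 39), 16 at 0.5 (26 − 10), 10 at 0.7 (14 − 4) and 3 at 0.15 (100 − 97). The actual loss depends on skewness, effect size and correlation, none of which the documents give.

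Three stronger readings are not supported. Scale does not create a false-positive risk, because the raw-scale test is conservative. A difference in pg/mL is not meaningless; it is an interpretable but less efficient summary when data are skewed. Aim 3 as a whole is not undermined, because it also rests on SOFA, an ordinal score to which the log-scale argument does not apply. No figure in the plan is wrong.

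**What to change.** State in the SAP that:

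- the nine biomarkers are analysed as log10 concentration, with a fixed rule for values below the assay limit;
- day 0 enters as a baseline covariate (or a constrained baseline), not as an outcome level;
- results are reported as geometric mean ratios (TH/control) with 95% intervals;
- these results are exploratory. Nine independent tests at 0.05 would give 1 − 0.95⁹ ≈ 37% chance of at least one false positive.

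Do not add hours from randomization as a plain covariate. At most, add a sensitivity analysis with a treatment-by-elapsed-time term, using the randomization and sample collection times already recorded on the case report forms.

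The cost is a few SAP sentences and a little more analysis work. No new data, samples or visits are needed. The one trade-off is that effects are read as ratios of geometric means and not as differences in pg/mL.

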## 1/ Study Overview

### 1.1/ Study Synopsis

There is both a rational theoretical basis and empiric preclinical and clinical data to support using therapeutic hypothermia (TH) as a new treatment modality for ARDS. Since the reduction in metabolism by TH plus neuromuscular blockade (NMB) to block shivering reduces the requirement for pulmonary gas exchange, TH+NMB will reduce exposure of vulnerable lung parenchyma to injurious mechanical ventilation as does low tidal volume ventilation and prone positioning. However, TH also directly dampen two cell signaling pathways that contribute to lung injury, Transient Receptor Potential Cation Channel Subfamily V Member 4 (TRPV4) and p38 Mitogen-activated kinase (MAPK). The additional effects of TH on pathogenic cell signaling suggests it will confer lung protection in ARDS that is additive with current therapies. Preclinical studies demonstrate that hyperthermia worsens and hypothermia mitigates animal models of ALI through effects on leukocytes and lung endothelium and epithelium. Clinical studies of temperature management in ARDS is still at an early stage, but an older small prospective non-randomized controlled trial of TH ( $33.7\pm 0.6^{\circ}\text{C}$  for  $70\pm 15\text{h}$ ) in moribund patients with septic shock and ARDS showed improved survival in the TH group (3 of 9 vs. 0 of 10). This study preceded modern definitions and management for ARDS and mortality rates in both groups were much higher than current experience. A trial of TH ( $35^{\circ}\text{C}$ ) vs. normothermia in 31 patients with renal transplant and respiratory failure due to infection showed improved patient and renal graft survival in the TH group, but no measures of lung function were included. Our CHILL historical-controlled open-label study of TH+NMB in patients with ARDS showed TH+NMB to be safe and to improve mortality and 28-day ventilator-free days (VFDs) compared with historical controls. Although these studies were not randomized control trial (RCT), they provide strong support for our hypothesis that TH+NMB will be lung-protective in ARDS. There is additional justification for TH in COVID-19. The early autopsy studies have shown pathophysiology that looks like ARDS. Many of the cytokines released during the cytokine storm associated with severe COVID-19 pneumonia and ARDS are reduced at clinically relevant hypothermic temperatures.

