## 8/ Study Interventions

### Temperature management:

1. Therapeutic Hypothermia Arm: The participating ICUs share an established institutional protocol for NMB and TH, which will facilitate rapid mobilization of treatment following randomization. Sedation will be adjusted to achieve a RASS -4 score and cisatracurium (Nimbex™) will be initiated and adjusted to the lowest rate that achieves nerve stimulation response of 2 twitches in train-of-four monitoring, reduction in ventilator dyssynchrony to acceptable levels, and elimination of shivering. NMB will be continued through the rewarming phase at least until core temperature reaches 35.5°C (~54h total time). Note that if the supply of Nimbex in the Clinical Pharmacy is insufficient to treat the subject, a supply of study-only Nimbex is available in the Investigational Drug Service Pharmacy.

Since the objective of CHILL-pilot is to test the effectiveness of cooling to a target temperature rather than the performance of a specific cooling device, patients in the TH arm will be cooled using one of the institution's two FDA-approved surface cooling devices, Blanketrol II cooling blankets or Arctic Sun™ cooling system. Core temperature will be reduced to 34°-35°C as quickly as possible and TH maintained for 48h. Patients will then be rewarmed to 36°C by 0.3°C/h and the cooling device removed. Post-cooling fever suppression is not part of the CHILL-pilot protocol. Cooling parameters were selected to optimize risk:benefit ratio. The criteria for early termination of hypothermia are persistent severe bradycardia (heart rate < 30 associated with mean arterial pressure <65 without vasopressor agents), uncontrolled bleeding, and intractable ventricular arrhythmias.

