- Collect blood and complete CRFs for Day 2, 3, 4, and 7 at 0800 on randomization day + 2, +3, +4, and +7 covering the prior 24h period

SITE ID		PATIENT ID				LETTER CODE			

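### The only test of lung physiology spans cooled and rewarmed days with no named day-3 contrast, so a reversible on-treatment fall, chiefly in OSI, can be read as lung protection

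*SAP*

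**What the plan says.** The SAP gives physiological and biomarker outcomes one sentence. The method is a mixed-model repeated-measures ANOVA, and its stated purpose is to "test for group differences for physiological and biomarker secondary outcomes over days 0, 1, 2, 3, 4, and 7". It specifies no interaction, no day-specific contrast, no handling of day 0 and no separation of readings taken during cooling from those taken after it.

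The protocol (section 1.2, Aim 2) states the lung-protection hypothesis for one time point: "improved day-3 driving pressure and OSI than the controls". The SAP does not carry that day into a test.

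On treatment timing, section 8 of the protocol says "Core temperature will be reduced to 34°-35°C as quickly as possible and TH maintained for 48h", and then "Patients will then be rewarmed to 36°C by 0.3°C/h and the cooling device removed". It puts NMB in the hypothermia arm at about 54 h in total, while controls receive NMB only as clinically indicated. The Study Synopsis (section 1.1) says that hypothermia with NMB "to block shivering reduces the requirement for pulmonary gas exchange".

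On data timing, the schedule at the end of the Screening/Enrollment/Randomization form in the Appendix sets the Day 2, 3, 4 and 7 forms at 0800 on the matching day after randomisation, "covering the prior 24h period". Ventilator and respiratory parameters are reference measurements taken between 0600 and 1000 (section 6).

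**The concern.** OSI is mean airway pressure × FiO2 × 100 / SpO2 (section 7.2). If cooling and paralysis reduce the demand for gas exchange, FiO2 and airway pressure can be turned down while they last, and OSI falls with no change in lung injury. An overall group comparison that averages such days with days after rewarming mixes an acute, reversible effect with the lasting one that a claim of lung protection needs.

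The SAP looks for trends toward benefit, and section 1.2 says the pilot should help show whether 48 h of cooling is enough. Both questions turn on what persists after rewarming, which the planned test does not isolate.

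**Working it through.** **1. The protocol's own timings.** Randomisation at 2359 puts 0800 next day at 8 h 1 min; at 0001 it is 31 h 59 min. Both match the Day 1 range printed on the form. For treatment length, 48 + (36 − T)/0.3 with T = 34–35°C gives 54.7–51.3 h to reach 36°C, and 53.0–49.7 h to reach 35.5°C. The protocol's figure of about 54 h is reproduced to within about 1 h at the 34°C end. Adding the 4 h that Aim 1 allows to reach target gives 55.3–58.7 h to 36°C.

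**2. Where the readings fall.** With randomisation at clock hour r, the Day k 0800 reading is 24k + 8 − r hours later. Assuming r is uniform over 24 h:

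| Day | Hours after randomisation | Share within 54 h |
|---|---|---|
| 1 | 8–32 | 100% |
| 2 | 32–56 | (54 − 32)/24 = 92% |
| 3 | 56–80 | 0% |
| 4 | 80–104 | 0% |
| 7 | 152–176 | 0% |

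If 36°C is reached only at 58.7 h, the Day 3 share is (58.7 − 56)/24 = 11%; Days 4 and 7 stay at 0%.

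The 24 h behind the Day 3 form run from 56 − r to 80 − r. With treatment ending at 54 h the overlap is max(0, r − 2), which averages 22²/(2 × 24) = 10.1 h, or 42% of the window. With an end at 57 h or 58.7 h it is 54% or 61%.

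**3. Effect on the test.** The documents give no SD, correlation or effect size for these outcomes. I assume:
- 10 per arm (20 patients, 1:1) with complete data;
- unit SD and equal within-patient correlation ρ;
- two-sided 0.05, which the SAP states only for the ventilator-free-day test;
- an effect d on days 1–2 and none on days 3, 4 and 7.

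With balanced complete data, the group main effect is a t-test (18 df) on patient means over p days. The mean difference is 2d/p, the variance of a patient mean is (1 + (p − 1)ρ)/p, and the noncentrality is (2d/p)/√(variance × 2/10). For d = 1 SD:

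| Days averaged | ρ | Difference | Variance | Noncentrality | Significant |
|---|---|---|---|---|---|
| Six | 0.3 | 0.33 | 0.417 | 1.15 | 19% |
| Six | 0.6 | 0.33 | 0.667 | 0.91 | 14% |
| Five post-baseline | 0.3 | 0.40 | 0.440 | 1.35 | 25% |
| Five post-baseline | 0.6 | 0.40 | 0.680 | 1.08 | 18% |

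Simulation (20,000 trials per setting) agrees with the formula. Over ρ = 0.3–0.7, the six-day rate is 7–9% for d = 0.5 SD and 37–59% for d = 2 SD. A contrast on day 3 alone, or on days 3, 4 and 7, rejects in 4.6–5.4% of trials in every setting. It also stays at about 5% (4.8–5.2%) with the day 0 value as covariate (ρ = 0.3 and 0.6, d = 1 SD).

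**The case against.** The strongest reply is that the protocol already has a usable time point. Day 3 at 0800 lies beyond 54 h, and driving pressure is a 0600–1000 point reading. That stands. It narrows the fault to the SAP's failure to adopt that day.

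Several stronger readings are tempting, and the documents do not support them:

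- **Day 3 is itself contaminated by 42–61%.** This holds only if daily OSI is built from all the 2-hour blocks. No section says so, and the block nearest 0800 could serve. It never applies to driving pressure.
- **The model cannot separate the two effects.** A mixed model over listed days can give day-specific estimates. The SAP just does not specify any.
- **A group-by-day test would mostly give false positives.** Under the 1 SD scenario it rejects in 62–96% of trials, but that is power to detect an effect that really does fade. It does show that adding an interaction test alone would not answer the lung-protection question.
- **On-treatment change is mere artefact.** Section 1.1 counts less exposure to injurious ventilation as part of the protective mechanism, so days 1–2 deserve reporting. Alone they cannot show a lasting effect.
- **Driving pressure is equally exposed.** Section 7.2 defines it on a breath without spontaneous effort, so the oxygen-demand argument bears mainly on OSI.

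The stakes are also modest, since these are secondary outcomes in a 20-patient feasibility pilot.

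**Conclusion.** The concern holds in this limited form. Two of the five post-baseline days are almost wholly on treatment, the protocol predicts a reversible change on them, and the SAP names no contrast that sets them apart. A purely transient effect d appears in the six-day group difference as d/3. At 1 SD that yields a significant overall result in about 14–19% of trials (18–25% over the five post-baseline days), against 5% for a post-rewarming contrast.

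These rates depend on the assumed effect, on correlation 0.3–0.6 and on complete data; readings lost to extubation or death were not modelled. They are not type I error rates in the strict sense, because the effect on days 1–2 is real. They measure how often it could be taken for lung protection. The timing rests only on the protocol's clock and evenly spread randomisation. The change should be made, but it does not touch the primary outcome, the serious-adverse-event comparison or the ventilator-free-day test.

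**What to change.** In the SAP, keep the mixed model and specify it:

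1. Fit group, day and group-by-day, with the day 0 value as covariate rather than as an outcome.
2. Name the group contrast at day 3 as the Aim 2 test of lung protection, supported by days 4 and 7.
3. Define the readings. For driving pressure, use the 0600–1000 value. For OSI, use the block nearest 0800, not a 24-h average. The Day 07 form has 6-hour blocks ending at 0600, so say which block applies there.
4. Report days 1–2 separately as on-treatment physiology.
5. Do not select readings by NMB status. That conditions on a post-randomisation state, and plateau pressure has no time field on the daily forms.
6. As a sensitivity analysis, drop day 3 and use days 4 and 7, to cover the up to about 11% of day-3 readings that could precede 36°C.

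The day labels on the forms must also be reconciled, because the contrast depends on them. The Day 03 and Day 04 forms are headed as collected on day 2 after randomisation. The lung-physiology blocks on the Day 03, 04 and 07 forms also say day 2. Both disagree with the Appendix schedule.

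The cost is SAP wording and corrected form labels, with no new data collection. Using fewer days loses some precision, and fewer patients will still be ventilated with readings at days 4 and 7. Under the same assumptions, a lasting 1 SD effect would be detected at day 3 alone with 56% power (noncentrality 1/√0.2 = 2.24). The average of days 3, 4 and 7 has 69–83% (variance (1 + 2ρ)/3, noncentrality 2.61–3.06), before any gain from the baseline covariate.
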